The supplements to be tested in TOHP include calcium, magnesium, potassium, and fish oil (the only agent for which an Investigational New Drug approval is necessary). For subjects in the supplements arm of the trial, the total study period will be divided into two sequential phases of six months duration interrupted by a three-month wash-out period during which subjects will be maintained on placebos of their assigned Stage 1 agent. A set of entry and termination BP measurements will be obtained for each of the active intervention phases. Calcium and magnesium will be tested during Stage 1. Participants will be randomized to one of four regimens: calcium, magnesium or their respective placebos. Since the placebo controls are shared (i.e., the same group of controls serves as the comparison series for both the active calcium and the active magnesium groups), approximately half of those randomized to the control

group will receive placebo calcium and the other half will receive placebo magnesium. For Stage 2, participants who are still willing and eligible to continue will be randomly assigned to either fish oil, potassium, or their respective placebos. As with Stage 1, the placebo controls will be shared.

1. Dosages

The dosages selected for calcium, magnesium and potassium represent an approximate doubling of usual dietary intake in Western countries. The dose of fish oil is equivalent to that which would be obtained by ingesting approximately a half pound of salmon per day and is consistent with a level of supplementation that could be achieved by diet. The specific dosages and number of daily pills required for each of the supplements are as presented in Table 11.

All supplements will be administered in two doses per day, taken in the morning and evening, as this schedule is more convenient for participants than more frequent administration and thus more likely to enhance compliance. For calcium, magnesium, and fish oil, the pills will be divided into two equal doses. For potassium, participants will be instructed to take two pills in the morning and one in the evening to minimize the likelihood of esophageal irritation. A missed morning dose can be made up in the evening, and a missed evening dose can be made up the following morning; however, participants should never take more than a full daily dose at one time.

2. Run-In

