Termination data for Stage 1 will be collected at three visits (7-30 days apart) scheduled at the conclusion of Stage 1 and beginning with the 6-month follow-up visit. In addition to study-wide termination measurements, participants will be asked whether they thought they were taking active or placebo pills. At the final termination visit, calendar packs will be collected and new cards will be dispensed to each subject for pill-taking during the wash-out period. These cards will contain placebo components of the participant's Stage 1 assignment. A follow-up appointment will be scheduled in approximately three months for the collection of eligibility information for Stage 2.

Eligibility on BP for Stage 2 will be re-evaluated at three eligibility visits scheduled 7-30 days apart at the conclusion of the wash-out period. At each of the visits, DBP will be determined as an average of all BPs obtained up to that time at the eligibility visits (three per visit) with the average falling within specified ranges. New baseline data will also

be collected at these visits. There will be some participants who no longer satisfy the original BP eligibility criteria for entry into the trial, or who might have other reasons for disqualifaction, such as noncompliance or use of BP-lowering medications. However, participation in Stage 2 will be available to all Stage l participants, as part of the original understanding at the time of signing the informed consent. domization at entry into the Stage 2 will be stratified as follows: stratum for those meeting the qualifications as described in the protocol, a stratum for those whose BPs are now too low to meet the original criteria, and a stratum for those with any other reason for disqualification. The analyses will exclude the latter two groups, except for descriptive purposes. Participants who are willing will be randomized to either fish oil, potassium or their respective placebos at a randomization visit scheduled within 10 days of the final eligibility visit. Randomization will proceed as for other treatment arms of the trial.

Termination data for Stage 2 will be collected at 3 visits (10 days apart) scheduled at the conclusion of Stage 2 and beginning with the 6-month follow-up visit.

The schedule of follow-up visits and data collection for the supplements interventions is shown in Table 3.

4. Measures to Enhance Compliance

The following measures will be taken to enhance pill compliance:

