a. Prior to Stage 2, individuals with a bleeding history will be identified based upon responses to the Supplements Form administered at SV3, SRV, 6 weeks, 13 weeks, and 26 weeks and reviewed by a clinic physician. Those individuals identified by the clinic physician as having a potential bleeding disorder based upon responses to the follow-up forms, will be asked to undergo evaluatory tests for

bleeding time, platelet count and VWF level for possible exclusion from Stage 2 based upon a history of recurrent abnormal bleeding.

- b. Individuals identified by the clinic physician as having a potential bleeding disorder, who do not wish to submit themselves to testing, will be excluded from Stage 2.
- c. During Stage 2, individuals assigned to the fish oil component who develop a bleeding history based upon responses to the Supplements form administered at 6 weeks and 13 weeks of Stage 2 or other self-reports will have their case reviewed by a clinic physician. If in the judgement of the physician it is clinically warranted, the individual will be asked to undergo tests immediately to evaluate the bleeding problem. Participants will be asked to discontinue their pills for the duration of the trial if, in the opinion of the clinic physician, the tests reveal an abnormal bleeding problem or if the participant refuses to undergo the recommended evaluation procedures.

ASCERTAINMENT OF ENDPOINTS

Both primary and secondary outcomes for TOHP are determined from measurements and laboratory tests taken at follow-up visits; therefore, ascertainment of endpoints is relatively simple and straightforward. Outcome measurements will be made by data collectors blinded to the treatment assignment of participants and not involved in delivering any lifestyle intervention. Due to the subjective nature of BP measurement, it is particularly important that the BP observers are not involved in any way with the delivery of any intervention and have no access to intervention-specific data. Insofar as possible, data collection visits should take place on different days and at different locations from intervention visits so that those in the active intervention groups do not become more habituated to the data collection environment than those in the comparison group.

Ascertainment of Blood Pressure

The outcome of primary interest, for which the sample size and power calculations were performed, is diastolic BP; a major secondary endpoint is

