At SV3 only, to be collected and stored for all lifestyle participants at clinics offering weight loss. At the 12 and 18 month follow-up visits, to be collected and stored for weight loss and high weight control groups only (central laboratory)

d
To be collected and stored at the central lab for all lifestyle and control
participants, with a sample of sodium, stress, and control groups to be analyzed,
pending availability of funds

Table 5

BLOOD AND URINE TESTS FOR SUPPLEMENTS INTERVENTIONS

	Š	Stage 1 (Ca	1 (Calcium and Magnesium) FOLLOW-UP VISI	and Magnesium) FOLLOW-UP VISITS	ge 2 eline	nd Fi OW-UP	ii)
BLOOD Sorum calcium	SV3	SRV	3-Month	6-Month	EL3 Xa	3-Month 6-Month	uth .
Serum glucose	m×						
Serum creatinine	×a				×a		
Serum potassium	×				×a		
Serum magnesium	×		×q	×q			
Total cholesterol	×				e ×		
Plasma and serum samples*	×						
Plasma fatty acid phospholipids	ds	-	-		×	×°°×	-
Plasma sample for possible lipid analyses					×	q ^X q ^X	
URINE Creatinine	×	×	×	×	×	×	
Sodium	×	×	×	×	*	×	
Potassium	×	×	×	×	×	× ×	
Magnesium	×	×	рx	px			
Calcium	×	×	×e	×e			
a For eligibility (local labou	laboratory)		N W	Note: All of the all participants	of the above plasma and pants in the supplements	serum samples	are drawn

a For eligibility (local laboratory)
b Fish oil and control groups only
c 50% sample of fish oil and control groups only
magnesium and control groups only
c Calcium and control groups only

specific assays are performed on all or a sample of participant all participants in the supplements intervention; analyses for as described in the footnotes.

To be collected and stored for possible future analyses.

Table 6
OUTLINE OF THE LOW-SODIUM INTENSIVE INTERVENTION SESSIONS

SESSION	THEME
Individual	Welcome
Group 1	'First Taste'
Group 2	'The Big Picture'
Group 3	'Starting Early'
Group 4	'New Approaches to Lunch'
Group 5	'The Best Meal of the Day'
Individual	Problem Solving
Group 6	'Sodium and Social Life'
Group 7	'Putting it all Together'
Group 8	'Keeping up with a New Lifestyle'

Monthly Maintenance Sessions

Table 7 SCHEDULE OF INDIVIDUAL AND GROUP CONTACTS IN THE LOW SCITCH INTERVENTION

Scre	ening		Rando	mizati	.on	Inter	nsivo	Intervo	ntion	Phase			
			Weeks	:									
								~					
SV1	SV2	SV3	SRV	1	2	3	4	5	€	7	8	9	10
			INDl		CT. 7			IND2		-			
				GF1	GF I	GP3	GP4		GP 5		GPó		GP?

IND = Individual contact

.GP = Group contact

'TR	AN	SITI	ON'				MAINTE	NANCE				END
Mon	th	s:										
3		4	6 .	8	10	12	14	⁻ 16	18	2C	22	24

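### Stage 2 is open to all willing Stage 1 participants, with no stated bar before randomization for those who should not be given potassium

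*Protocol*

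**What the plan says.** Clinic Procedures, under Supplements in Intervention Methods, expects that by Stage 2 some participants will no longer meet the blood pressure criteria. Others will be disqualified for different reasons, "such as noncompliance or use of BP-lowering medications". It then states that "participation in Stage 2 will be available to all" Stage 1 participants, citing the understanding at consent. Randomization has three strata: those who qualify, those whose pressure is now too low, and "a stratum for those with any other reason for disqualification". The last two are analysed only descriptively. The assignment rule is: "Participants who are willing will be randomized to either fish oil, potassium or their respective placebos". Assignment happens on a separate occasion, no more than 10 days after eligibility screening ends.

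Four other places bear on this:

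- **Supplements, opening text:** "For Stage 2, participants who are still willing and eligible to continue will be randomly assigned".
- **Supplements, Side Effects (fish oil safety, item b):** people with a possible bleeding disorder "who do not wish to submit themselves to testing, will be excluded from Stage 2".
- **Table 5:** the Stage 2 baseline column (EL3) appears to carry footnote a against serum potassium and creatinine. The footnote begins "For eligibility (local laboratory".
- **Safety Monitoring:** potassium supplementation is named as contraindicated in people placed on potassium-sparing diuretics.

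**The concern.** The assignment rule in Clinic Procedures has one condition, willingness, and withholds potassium from no stratum. Someone taking a potassium-sparing diuretic is a user of a blood-pressure-lowering drug, so the text admits that person by name and then allows assignment to potassium. A participant whose EL3 potassium or creatinine fails the entry criterion falls in the same catch-all stratum.

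What is at stake is participant safety and a clear instruction to the clinics. The potassium dose is 60 mmol/day (Table 11: 3 pills of 20 mmol), which the Dosages text describes as roughly doubling usual intake, and it is given under code. Because that stratum is not analysed for efficacy, those exposed would carry the risk without adding to the comparison.

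**Working it through.** This is mainly a comparison of texts. The arithmetic only sets a scale.

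**1. Who may be randomized in Stage 2**

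| Place in protocol | Condition | Effect of a disqualification |
|---|---|---|
| Supplements, opening text | willing and eligible | not randomized |
| Clinic Procedures | willing | separate stratum, randomized, not analysed |
| Side Effects, item b | bleeding work-up not refused | excluded from Stage 2 |

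The first two rows cannot both be followed for a disqualified but willing participant. The third is an exception that Clinic Procedures does not mention.

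**2. Is there a bar before randomization for potassium?**

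- *Potassium-sparing diuretic.* Diuretics are an entry exclusion (Exclusion Criteria, item 13). The Safety Monitoring contraindication qualifies advice to stay on an intervention already assigned. It is not written as a condition of Stage 2 randomization, and Clinic Procedures does not refer to it.
- *Serum potassium and creatinine.* Both are entry exclusions: item 17 (unexplained hyperkalemia) and item 15 (creatinine of 1.7 mg/dl or more in men, 1.5 in women). Safety Monitoring also lists elevated potassium among the exclusions meant to keep out people at particular risk. The only stated rule that covers a failed EL3 value is the catch-all stratum, which is randomized.

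**3. Rules that shrink the group**

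- Under Ascertainment of Final BP Measurements, item a, a participant whose physician treats raised pressure after the termination readings leaves the study.
- For hypotensive drugs started for other reasons, the same item asks for termination readings but does not say that the participant leaves.
- Safety Monitoring has a missed visit form completed for participants placed on antihypertensive drugs, and encourages full involvement again after two months off them.

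None of these is a bar at Stage 2 randomization, and Clinic Procedures itself expects medicated participants to be there.

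**4. Scale**

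Table 1 plans 207 + 199 + 203 = 609 for Stage 2. Its footnote rule gives 0.85 × 698 + 18 = 611.3, close enough for this purpose. The share on active potassium is 207/609 = 0.340.

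The documents give no rate for the problem. The rates below are assumed, as is the use of the Table 1 allocation in the non-analysed stratum.

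| Assumed share affected | Of 609 | On active potassium | Of all 698 from Stage 1 | On active potassium |
|---|---|---|---|---|
| 0.5% | 3.05 | 1.04 | 3.49 | 1.19 |
| 1% | 6.09 | 2.07 | 6.98 | 2.37 |
| 2% | 12.18 | 4.14 | 13.96 | 4.75 |

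**5. Primary analysis**

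The stratum concerned is already outside the analyses, so barring these people from potassium removes no one from the efficacy comparison.

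**The case against.** The strongest reply is that the protocol, read as a whole, already deals with this.

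- **A specific rule qualifies a general one.** The bleeding exclusion is a specific safety rule in the same Supplements section and reads naturally as an exception to open access. This stands: for bleeding, a missing cross-reference is the most that can be claimed. A reader might infer a flat contradiction there, but the text does not require one.
- **Eligibility at EL3 may mean stratum assignment.** That is a fair reading, and on it Table 5 does not contradict open access. It still leaves a failed potassium or creatinine with no consequence for what the participant may be given.
- **Stage 2 randomization follows the usual process.** Clinic Procedures says so, and at entry that process includes Coordinating Center eligibility review and stopping pills in ineligible people. But here the text expressly randomizes the disqualified, so that review would naturally decide the stratum and not bar entry.
- **Staff would notice.** Probably in most cases. The written rule still points the other way.
- **Later blood tests.** A reader might infer that EL3 is the only potassium and creatinine check after entry. The documents do not support that. Table 5 has lost its column alignment, Table 3 shows blood samples in Stage 2 follow-up, the follow-up schedule says follow-up bloods serve mainly compliance and safety monitoring, and Safety Monitoring says both analytes are checked periodically.
- **Unseen documents.** The consent pages and the Manual of Operations are not available and might add limits.

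**Conclusion.** The point holds, at low severity. As written, Clinic Procedures opens Stage 2 to every willing Stage 1 participant, conflicts with the opening Supplements text, and sets no bar before randomization for the potassium-sparing diuretic contraindication or for a failed EL3 potassium or creatinine. The last part depends on Table 5 having been read correctly.

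The number exposed is unknown and probably small. On assumed rates of 0.5% to 2% it would be about 1 to 5 people on active potassium. There is no effect on the primary analysis.

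Three stronger readings are not supported:

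- Raised potassium and creatinine are entry exclusions. The protocol does not name them as contraindications to potassium.
- Nothing shows a deliberate choice to give potassium to people in whom it is contraindicated. Admitting low-pressure and noncompliant participants in non-analysed strata is deliberate and is not criticised.
- The named contraindication concerns potassium alone. It does not justify requiring that these people be kept out of Stage 2 altogether, or adding new checks on fish oil.

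**What to change.** Amend the Stage 2 text in Clinic Procedures so that open access is subject to two conditions:

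1. The bleeding exclusions under Side Effects apply.
2. Anyone currently using a potassium-sparing diuretic, or failing the entry criterion for serum potassium (item 17) or creatinine (item 15) at EL3, enters no randomization that could assign potassium. EL3 results are reviewed before randomization. These participants may be offered fish oil or its placebo only, within the non-analysed stratum, or be left out of Stage 2.

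All other disqualifications continue to decide the stratum only. Bring the opening Supplements text into line.

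The cost is a wording change with no new test or visit and no loss to the primary analysis. There are two downsides. The Stage 2 offer becomes slightly narrower than the consent understanding implied. Randomization may also have to wait for the EL3 results, because the 10-day window sets no minimum interval and eligibility review at entry is allowed five working days. Item 17 has no numeric limit in the protocol, so the local laboratory's definition would apply, as it does at entry.

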The above analyses have been concerned with comparing mean change in DBP among different treatment groups. However, it is well known that effects of intervention are not uniform across all members of an actual intervention group. Furthermore, some members of the control group may seek to implement some of the intervention strategies on their own (such as weight reduction or sodium restriction). Therefore, as a secondary analysis mean changes in DBP will be examined as a function of changes in risk factors that should be affected by the interventions strategies (such as weight loss, changes in urinary sodium or potassium) regardless of treatment assignment.

Another issue that is a characteristic feature of hypertension trials performed on normotensive subjects is that some subjects have BP elevations sufficient to cause their physician to prescribe antihypertensive medication and to withdraw from the trial. These persons are crucially important to the study, since exclusion of such individuals will result in a biased estimate of effects of specific interventions. Therefore, several strategies will be employed to deal with the effects of such censored data, including the use of mean change in DBP

from entry to the relevant visit in the trial, and use of more sophisticated censored data methods to estimate what change in DBP would have occurred had such participants been left untreated and followed. For this purpose, upon untimely termination of a participant from the trial, we will obtain nine readings over three termination visits to better characterize BP changes in such persons.

Another issue that will be monitored on a regular basis is compliance of subjects with the intervention modalities. This will be analyzed by looking at changes in physiologic parameters that should be affected by the actual interventions (such as urinary sodium or potassium and body weight). Measures of compliance will be developed and assessed throughout the trial.

Finally, we will perform safety monitoring in the trial, with particular emphasis on the nutritional supplement interventions to compare side effects reported by the treated and placebo groups. Both safety and efficacy data will be analyzed every six months for purposes of review by the Data and Safety Monitoring Committee (or more frequently, if requested).

STUDY ORGANIZATION

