- To coordinate communications among the centers;
- To assist in training clinic staff in study procedures;
- To coordinate certification of the clinical center staff;
- To oversee the random assignment of each study participant to one of the intervention or control regimens;
- To review all study data for completeness and accuracy;
- To monitor the performance of all participating units;
- To prepare periodic reports on the performance of the clinics;
- To analyze frequency of specified events and any adverse reactions by intervention group and to report these data to the Data and Safety Monitoring Committee;
- To prepare recruitment, technical, and statistical reports for the meetings of the Steering Committee and the Data and Safety Monitoring Committee;
- To assist in the preparation of scientific reports for publication.
- 3. National Heart, Lung and Blood Institute

The NHLBI has overall responsibility for the scientific and fiscal management of TOHP. The NHLBI Project Officer is a voting member of the Steering and Executive Committees of TOHP, as well as a non-voting member of the Data and Safety Monitoring Committee.

4. Central Laboratories

All urine and blood analyses except for phospholipids will be performed by [name] at the University of Minnesota School of Public Health in Minneapolis, which will also store additional plasma and serum samples for possible later analyses. Blood phospholipid analyses will be performed by [name] at the Channing Laboratory in Boston.

Study Administration

The administrative structure of TOHP consists of a series of committees and subcommittees which include representatives from all the participating units.

1. Steering Committee

The Steering Committee is the central governing body of TOHP. It is made up of the principal investigators, interventionists, and coordinators from each of the clinical centers as well as representatives from the CC and NHLBI. Each participating unit has one vote normally cast by the Principal Investigator. The Steering Committee meets at least semi-annually to review the progress of the trial. Each center is required to be represented at each meeting by at least the Principal Investigator (or designated co-investigator) and one other representative from that clinic. The Study Chairman serves as chairman of the Steering Committee.

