The TOHP Executive Committee, is made up of the chairmen of the five sub-committees of the Steering Committee, the NHLBI Project Officer, the CC director, and the study chairman. This group discusses and helps to formulate and implement all Steering Committee decisions related to the conduct of TOHP within the guidelines established by the protocol.

Specific functions of the Executive Committee include:

- Resolving any operational problems that arise between Steering
 Committee meetings, consulting with the principal investigators if appropriate;
- Advising and assisting the CC on operational matters;
- Preliminary review of the performance of all participating centers on the basis of reports provided by the CC.

The Executive Committee meets in advance of the meetings of the Steering Committee and as necessary on other occasions.

11/7/88

3. Data and Safety Monitoring Committee

The Data and Safety Monitoring Committee (DSMC) is responsible for reviewing the initial study protocol, for assessing accumulating study data for adverse and/or beneficial intervention effects, and for seeing that risks to subjects are minimized. As part of this responsibility for minimizing risk to participants, the DSMC reviews procedures for data surveillance to assure that these are sufficient to identify the occurrence of adverse events in any intervention group. This review includes receiving monitoring reports prepared and supplied by the staff of the CC for evidence of adverse or beneficial intervention effects. After review of each report, the DSMC is responsible for making specific recommendations to the Steering Committee and the NHLBI about whether to continue the study, with or without changes in the protocol, or to stop the trial. The DSMC is also charged with advising the Steering Committee and NHLBI on whether to proceed with Phase II of TOHP. Votes at meetings are identified and recorded by individual response.

-62-

The DSMC members are appointed by the NHLBI Project Office based on consultation with the Executive Committee. The voting members represent skills in cardiovascular disease epidemiology, trial methodology, biostatistics, nutrition, behavioral science, and bioethics. The study chairman, CC director, and NHLBI Project Officer serve as non-voting members. A complete membership listing of this committee is contained in Appendix B.

Members of the DSMC are expected:

- To acquire a detailed knowledge of the TOHP design and goals;

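### Stage 2 randomizes two disqualified strata, then excludes them from all but descriptive analyses with no exception for safety, which conflicts with the protocol's unrestricted side-effect comparison

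*Protocol*

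**What the plan says.** The rule stands in the protocol under Intervention Methods, Supplements, in the clinic procedures for Stage 2. Entry is open: "participation in Stage 2 will be available to all Stage l participants, as part of the original understanding". Randomization uses three strata. One holds those who still qualify. The other two are worded as follows: "a stratum for those whose BPs are now too low to meet the original criteria, and a stratum for those with any other reason". What can disqualify a participant is given by example: "such as noncompliance or use of BP-lowering medications". The sentence on analysis follows directly: "The analyses will exclude the latter two groups, except for descriptive purposes".

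Two other places set out the safety analysis. Data Analyses plans safety monitoring with "particular emphasis on the nutritional supplement interventions to compare side effects reported by the treated and placebo groups". Study Organization gives the Coordinating Center the task "To analyze frequency of specified events and any adverse reactions by intervention group" and has it report the result to the Data and Safety Monitoring Committee. That committee reviews the surveillance procedures "to assure that these are sufficient to identify the occurrence of adverse events in any intervention group". None of these mentions the Stage 2 strata.

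Table 1 and Table 12 project 207 participants on potassium, 199 on fish oil and 203 on placebo, 609 in all. They are not split by stratum.

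**The concern.** The exclusion is written for the analyses as a whole, and its single exception is descriptive use. There may be good reason to keep these strata out of the DBP comparison, since the trial's question concerns people with high normal pressure. The protocol gives no reason that would carry over to side effects. Participants in the excluded strata are randomized, take the same pills for six months, and have a concurrent placebo group within their own stratum. A valid randomized safety comparison therefore exists in them.

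An analyst who follows the Stage 2 text would drop them from that comparison. One who follows Data Analyses and Study Organization would keep them. At stake are the size of the randomized safety comparison and whether it covers everyone exposed.

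**Working it through.** **Step 1: the passages side by side.**

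| Place | Who is covered | Limited by stratum? |
|---|---|---|
| Supplements, Stage 2 randomization | all analyses except descriptive | yes, two of three strata out |
| Data Analyses, safety paragraph | treated and placebo groups | no |
| Study Organization, Coordinating Center | adverse reactions by intervention group | no |
| Safety Monitoring | side effects on all follow-up forms | no |

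The data are collected on everyone. Only the rule on who enters the comparison is inconsistent.

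**Step 2: the plan's own figures.** The protocol states no figure for the excluded share, so the inputs to a projection are checked first.
- Variance of a nine-reading mean DBP: 109.11 + 26.76/3 + 7.42/9 = 118.85, as stated.
- Observed six-month correlation: 0.92 × 109.11/118.85 = 0.84, as stated.
- Variance of six-month change: 2 × 118.85 × (1 − 0.84) = 38.03, as stated.
- Table 12 power for 2 mm Hg with SD 6.17: 0.907 for potassium (stated .91) and 0.901 for fish oil (stated .90). The table therefore uses the full projected numbers.

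**Step 3: projected share outside 80-89 mm Hg at re-eligibility.** The projection is a simulation from the protocol's variance components. People are selected through the three screening ranges (75-97, 77-94, 80-89 mm Hg on 3, 6 and 9 readings). A new nine-reading mean is then drawn with a true correlation of 0.92 (the protocol's six-month value) or 0.90 (its 18-month value); re-eligibility falls between those times. The source-population mean is not in the protocol and is varied.

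| Assumed mean (mm Hg) | Correlation | Below 80 | 90 or above | Outside |
|---|---|---|---|---|
| 72 | 0.92 | 36% | 11% | 47% |
| 72 | 0.90 | 37% | 12% | 49% |
| 78 | 0.92 | 28% | 15% | 44% |
| 78 | 0.90 | 30% | 16% | 46% |
| 80 | 0.92 | 26% | 17% | 43% |
| 80 | 0.90 | 28% | 18% | 45% |
| 84 | 0.92 | 22% | 21% | 43% |
| 84 | 0.90 | 23% | 22% | 45% |

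Rows may not add because of rounding. The range is 43% to 49%.

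**Step 4: what this means in people, if 609 covers all strata.**
- Everyone: 609 × 0.43 = 262 to 609 × 0.49 = 298; at 45%, 274.
- On active pills (207 + 199 = 406): 175 to 199; at 45%, 183.
- Precision: removing a share f from every arm multiplies the standard error of a treated-versus-placebo difference by 1/√(1 − f), at equal event rates. For f = 0.43, 0.45 and 0.49 this is 1.32, 1.35 and 1.40.

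**Step 5: the other reading of Table 12.** The footnote says 85% of Stage 1 participants are rerandomized, plus 6 per group at Baltimore. If that 85% meant the fully eligible stratum only, the excluded strata would have to come from the remaining 15% of 698, at most about 105 people, and would be additional to the 609. The protocol does not say which is meant.

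**The case against.** The strongest reply is that the sentence sits in a paragraph about blood pressure eligibility and new baselines, so its natural subject is the blood pressure outcome. The safety texts carry no stratum limit, side effects are asked about on all follow-up forms, bleeding on fish oil is reviewed case by case, and descriptive use could include side-effect tables by assigned group. Much of this stands. The protocol does not state that the side-effect comparison omits these people, and a reader who concludes that it plans to leave out nearly half of those exposed goes further than the text. What remains is a stated rule, without a safety exception, that contradicts the comparison promised elsewhere. Descriptive tables do not by themselves replace "to compare side effects reported by the treated and placebo groups".

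Three further inferences are tempting and unsupported:
- **That side effects would go unseen.** The chance of observing at least one case of a 1% event on fish oil is 1 − 0.99^199 = 0.86 with all 199, and 1 − 0.99^110 = 0.67 with about 110. But individual monitoring and descriptive reporting would still show a case in an excluded stratum. What shrinks is the formal contrast.
- **That the excluded people are those most likely to have side effects.** The projected share comes from DBP alone, and on most of the assumed means the larger part is people now below 80 mm Hg. Participants on BP-lowering drugs are not counted in it, and their number is not given.
- **That 45% is a fact of the plan.** The protocol says only that there will be some such participants.

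It can also be said that a safety population is usually left to the statistical analysis plan. That would answer silence. Here the protocol states a rule.

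**Conclusion.** The concern holds as a conflict within the protocol. Taken literally, the Stage 2 exclusion removes randomized, exposed participants from a side-effect comparison that other sections promise without restriction. The projected 43% to 49% rests on the protocol's variance components and tracking correlations, an assumed source-population mean of 72 to 84 mm Hg, normality, and no lasting Stage 1 effect on DBP. It leaves out noncompliance and drug use, which would add to it. It also assumes that everyone outside the range enters Stage 2; some of those with high readings may already have been terminated under Safety Monitoring. The head count of about 270, with about 180 on active pills, holds only if the 609 covers all strata. The conflict itself depends on none of these assumptions.

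A separate inconsistency touches the same stratum. The Stage 2 text randomizes participants who use BP-lowering medications to potassium, fish oil or placebo without qualification. Safety Monitoring names potassium supplementation as contraindicated for people placed on potassium-sparing diuretics. The two passages must be reconciled.

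**What to change.** Limit the exclusion sentence to the DBP and SBP outcome analyses. Add that Stage 2 side effects are compared by assigned group, stratified by the three randomization strata, in everyone re-randomized who took Stage 2 pills. State in the footnotes to Tables 1 and 12 whether the 85% covers all strata or only the eligible one. Reconcile the Stage 2 randomization text with Safety Monitoring for participants on BP-lowering medications; which rule should apply is a matter for the investigators.

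The analysis change costs a sentence and one stratified table. The side-effect data are already collected on all follow-up forms, and no visit or procedure changes.
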